For this pilot, we propose to consent up to 24 Veterans age 60-95 years with chronic musculoskeletal pain with the goal of having 18 Veterans initiate vEAET treatment (i.e., planning for at least 25% dropout, consistent with our prior studies). Modest funds will be used from the PI's Career Development Award to provide a tablet for each Veteran. Each Veteran will receive one 90-minute individual session of vEAET plus eight 90-minute weekly group sessions of vEAET, all delivered over VTC to Veterans' homes. The study will plan to include 3 vEAET groups, each with 6 Veterans. We will use VA Video Connect (VVC) as the primary VTC platform, with Zoom Version 5.0 (Zoom Video Communication, San Jose, CA) as the back-up platform. Assessments will include satisfaction ratings, pain ratings, and psychosocial functioning, and will be performed at baseline, posttreatment, and 2-month follow-up. We will perform all assessments remotely using OutcomeMD (Los Angeles, CA), a HIPAA-compliant and VA-approved web-based platform. The goal is to perform the entire study remotely without any in-person visits. The Specific Aims are:

1. Acceptability and Feasibility. In 18 Veterans age 60-95 years with chronic musculoskeletal pain, assess recruitment, treatment adherence, treatment credibility, and patient satisfaction to vEAET.
2. Limited-Efficacy Testing and Estimated Effect Size. Assess the effects of vEAET on pain severity, pain interference, psychosocial functioning, depression, anxiety, and social connectedness from baseline to posttreatment and 2-month follow-up and calculate estimated effect sizes for a subsequent RCT.
3. Select Measures for Mediation/Moderation of Treatment Response. Veterans will complete validated measures on pain attitudes, cognitive/behavioral coping, and technological literacy to determine the feasibility of using these measures for future assessment of mediation/moderation in a subsequent RCT.

2. Background/Significance

Chronic pain is one of the most common and costly conditions treated at VA. Rates of chronic pain peak during late middle-age and older adulthood, reaching rates as high as 80% in older Veterans (1, 2). Given the recent "opioid crisis," DoD and VA have prioritized non-pharmacologic treatments as first line for chronic pain, and evaluation of non-pharmacologic treatments for chronic pain is a VA ORD priority area (3).

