One promising non-pharmacologic treatment for Veterans with chronic pain is EAET, which emphasizes emotional processing and improving interpersonal functioning for the rehabilitation of chronic pain (4). EAET has shown medium-to-large effect sizes for pain reduction in controlled and uncontrolled trials, including some superiority to CBT for adult non-Veterans with fibromyalgia (4, 5). In a clinical trial at GLA, we found that older Veterans (mean age=73.5 years) with chronic musculoskeletal pain who completed 1 individual session and 8 group sessions of in-person EAET compared to Veterans who underwent the same number of sessions of in-

person CBT had significantly lower pain severity at posttreatment and 3-month follow-up with a large effect size difference and marginally lower pain interference posttreatment ($p=0.051$) (6).

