Data Sources and Instruments. Self-report data are collected using a secure, HIPAA-compliant, and VA-approved web-based platform called OutcomeMD (Los Angeles, CA). Self-report data are collected at 4 time points: baseline, immediately after the individual session (treatment credibility only), posttreatment, and 2-month follow-up. The RC enters the OutcomeMD provider portal, selects the appropriate assessments, and sends a link to the email address created for the Veteran by the study, based on the Veteran's study-assigned alphanumeric code. This email address will be set up for the Veteran as part of the configuration of their tablet and mailed to them with it. Veterans click on the link, which opens directly to the assessments in their computer/smartphone web browser; no login or additional information is required from the Veteran. The Veteran's responses to assessments are sent electronically to the OutcomeMD provider portal, which are immediately extracted into an Excel spreadsheet and labelled by the RC with the Veteran's alphanumeric code. In addition, a brief telephone interview will be conducted by a research team member ([name]) at baseline and posttreatment using VA-approved software (Audacity) directly onto our encrypted VA research server, and the number of words patients use to describe their feelings will be coded using a procedure described in (14). Descriptive measures collected at baseline include demographics (age, sex, race/ethnicity, marital status, education) and clinical characteristics (medical comorbidities, medications, psychiatric diagnoses, substance use). All self-report study variables and their associated measurement instrument are shown in **Table 1**.

Table 1: Self-Report Study Assessments				Base-line	Post-treat.	2-mo. f/u	Expected Direction of Change
	Variable	Measurement Instrument					
Acceptability	Patient Satisfaction	Satisfaction with Therapy and Therapist Scale—Revised (15)			√		
	Treatment Credibility	Credibility/Expectancy Questionnaire (16)		*			
Potential Efficacy	Pain Severity	Mean of 4 Brief Pain Inventory (BPI) Items (17):	Current Pain	√	√	√	↓
			Average Pain				
			Worst Pain – 7 days				
			Least Pain – 7 days				
	Pain Interference	PROMIS-Pain Interference CAT (18, 19)		√	√	√	↓
	Psychosocial and Physical Function	PROMIS-Global Health (20)		√	√	√	↑
	Social Connectedness	Social Connectedness Scale—Revised (21)		√	√	√	↑
	Depression	PROMIS-Depression CAT (22)		√	√	√	↓
	Anxiety	PROMIS-Anxiety CAT (22)		√	√	√	↓

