Global Improvement	Patient Global Impression of Change (PGIC) (23)			√	√	↑	
Potential Mediators	Beliefs about Pain	Survey of Pain Attitudes (SOPA) (24)		√	√	√	↓

	Cognitive and Behavioral Coping	Coping Skills Questionnaire (CSQ) (25)	√	√	√	↑
	Feeling Words	Feeling Word Telephone Interview	√	√		↑
	Self-Conscious Affect	Test of Self-Conscious Affect-3—Short Version (TOSCA-3)	√	√	√	↓
	Emotion Differentiation	Positive and Negative Affect Scale (PANAS)	√	√	√	↑
	Pain Catastrophizing	Pain Catastrophizing Scale (PCS)	√	√	√	↓
	Discomfort with Anger	Anger Discomfort Scale	√	√	√	↓
Potential Moderators	Age	Self-report of age in years	√			
	Digital Literacy	Functional Assessment of Currently Employed Technology Scale (FACETS) (26)	√			

*The Credibility/Expectancy Questionnaire will be completed immediately following the individual session.

Intervention: Video Teleconference Emotional Awareness and Exposure Therapy (vEAET). All participants receive a single, initial 90-minute individual session followed by eight 90-minute sessions in small groups of 6 Veterans over VTC. The conceptual model of EAET is based on 1) neurobiological research showing structural and functional relationships between emotional brain circuits (e.g., anxiety) and brain circuits dealing with pain; 2) experiential and psychodynamic theories and particularly the relationship between life stress, emotional coping, and symptoms (pain); 3) epidemiological evidence relating trauma/life stress to pain; and 4) research relating alexithymia, emotional expression, and emotional awareness to pain. We will use the individual session protocol developed by the PI (6) and the group EAET manual originally developed by Lumley and Schubiner (27) and adapted for older Veterans with chronic musculoskeletal pain by the PI (6). All sessions include handouts for in-session writing exercises and homework, which will be mailed to participants prior to the first session. The sessions include:

- Individual Session. Therapist introduces the therapy model, which links pain to interpersonal life stress, avoidance of difficult emotions, and brain changes. The patient provides a history of their pain, focusing on how pain has been affected by stress and emotions. A therapeutic alliance is developed around changing stressful interpersonal relationships and emotions to alleviate pain.

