Fidelity Monitoring. All vEAET therapy sessions will be video recorded for the purposes of fidelity monitoring. In this pilot, an RC will complete a standardized checklist (attached) on a randomly-selected 25% of sessions to ensure that the sessions covered targeted topics. This is performed for the purposes of quality assurance. Participants will consent to the production of video recording at the time of informed consent by completing HIPAA authorization. Videos are encrypted, labeled with an alphanumeric code, and produced using VA-approved software directly onto our encrypted VA research server protected by 128-bit SSL, the secure socket layer technology used for sensitive transactions on the web (pathway R:\RES_Geripsych_Research). The system is accessible only via the VA intranet and employs a hierarchical system of password protected logins, allowing differential access to project team members as appropriate to their roles. The PI and his team have extensive experience conducting studies that have required creating data systems such as this for encrypted electronic files.

Analysis Plan. Prior to performing the primary analyses, descriptive statistics and graphical summaries are obtained for all baseline measures to check for missing data, outliers, and the need for transformations or non-parametric methods, and to obtain characteristics of the sample. We will perform descriptive statistics (e.g., means, standard deviations, frequencies) to evaluate acceptability (satisfaction, credibility) and feasibility variables (attendance, time spent training on VTC equipment). To evaluate within-treatment effects on outcomes, we will use paired-samples t-tests comparing baseline to posttreatment and baseline to follow-up scores on all efficacy outcomes. Within-treatment effect sizes will be calculated using the formula: $d = (\text{post [or follow-up] } M - \text{baseline } M) / \text{SD of change scores}$. To determine the frequency of individual cases having improvement in pain, we use the standard metric of 30% improvement, as well as the moderately stringent criterion of 50% improvement, and the very stringent criterion of 70% improvement. If some missing values are present due to attrition, we use a conservative estimation approach by assuming no change from the previous assessment and replacing missing follow-up data with the last available point (i.e., last observation carried forward).

4. Safety

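### Last observation carried forward is labelled conservative, but the plan does not assure this for the 2-month comparison, nor for d at posttreatment

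*Combined protocol and SAP*

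**What the plan says.** The Analysis Plan in section 3 gives one rule for all attrition: "we use a conservative estimation approach by assuming no change from the previous assessment and replacing missing follow-up data with the last available point". It names no other method for missing data and no sensitivity analysis.

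The rule feeds "paired-samples t-tests comparing baseline to posttreatment and baseline to follow-up scores on all efficacy outcomes", and a within-treatment d defined as mean change divided by the SD of change scores. The same paragraph plans responder counts: "To determine the frequency of individual cases having improvement in pain, we use the standard metric of 30% improvement", with 50% and 70% as stricter cut-offs. It names no visit for these counts.

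On visits, Data Sources and Instruments states: "Self-report data are collected at 4 time points: baseline, immediately after the individual session (treatment credibility only), posttreatment, and 2-month follow-up". No efficacy score therefore lies between baseline and posttreatment. Table 1 marks "Patient Global Impression of Change (PGIC") at posttreatment and 2 months only.

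Aim 2 is to assess effects "from baseline to posttreatment and 2-month follow-up and calculate estimated effect sizes for a subsequent RCT", and section 5 (List of Anticipated Research Products) says the effect sizes will serve the RCT power analyses.

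**The concern.** Carrying the last value forward is cautious only when that value is no better than the one the Veteran would have had. For loss before posttreatment the last value is baseline, and the Veteran is credited with no benefit. For loss after posttreatment the last value is the posttreatment score, so at 2 months the Veteran is credited with everything gained by the end of treatment. Assuming no change from the previous assessment then means assuming that the gain lasted, which is part of what the 2-month visit is there to test.

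The plan treats both kinds of loss alike and calls the result conservative. A reader of the report or of the grant application would take the 2-month d as a floor, and nothing planned would let that reader check it.

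**Working it through.** **Inputs from the documents.** 18 Veterans are to start treatment; efficacy visits are baseline, posttreatment and 2 months; d = mean change / SD of change. I sign improvement as positive.

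**The plan's own attrition figure.** Section 1 sets a consent ceiling of 24 "with the goal of having 18 Veterans initiate vEAET treatment (i.e., planning for at least 25% dropout, consistent with our prior studies". This reproduces: 18 / (1 − 0.25) = 24. The 25% takes consented Veterans to Veterans who start. The documents give no rate of loss after the start and no split by timing.

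**Evidence on durability.** Section 2 reports that in-person EAET, compared with CBT, gave "significantly lower pain severity at posttreatment and 3-month follow-up with a large effect size difference". That is a difference between arms. It does not give the share of within-person gain kept, and it is not video delivery.

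**Bias in the 2-month mean.** With N analysed, and no assumption that lost and retained Veterans fare alike:

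bias = [ Σ over late losses (posttreatment change − true 2-month change) − Σ over early losses (true 2-month change) ] / N

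The first sum is positive, zero or negative as gains among late losses fade, hold or grow. The second term lowers the estimate if early losses would have gained and raises it if they would have worsened.

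**Effect on d.** For groups with size k, mean m and SD s: overall mean M = Σkm / N, variance = Σk(s² + m²) / N − M², d = M / SD. An early loss enters with m = 0 and s = 0.

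**Illustration.** Assumed, not in the documents: all 18 starters analysed, 4 lost, posttreatment gain 0.8, SD of change 1. In cases E to H the other 14 keep the full gain.

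| Case | True mean / SD / d | Carried-forward mean / SD / d | d under the rule |
|---|---|---|---|
| A. 4 late; everyone keeps half the gain | 0.400 / 1.000 / 0.40 | 0.489 / 1.014 / 0.48 | too high |
| B. 4 late; everyone keeps it all | 0.800 / 1.000 / 0.80 | 0.800 / 1.000 / 0.80 | right |
| C. 4 late; everyone's gain grows by a quarter | 1.000 / 1.000 / 1.00 | 0.956 / 1.003 / 0.95 | too low |
| D. 4 late; only they relapse to baseline | 0.622 / 1.054 / 0.59 | 0.800 / 1.000 / 0.80 | too high |
| E. 4 early; would have gained like the rest | 0.800 / 1.000 / 0.80 | 0.622 / 0.943 / 0.66 | too low |
| F. 4 early; true mean change 0 | 0.622 / 1.054 / 0.59 | 0.622 / 0.943 / 0.66 | too high |
| G. 4 early; true mean gain 0.2 | 0.667 / 1.031 / 0.65 | 0.622 / 0.943 / 0.66 | slightly too high |
| H. 4 early; true mean worsening 0.4 | 0.533 / 1.118 / 0.48 | 0.622 / 0.943 / 0.66 | too high |

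For case A: M = (14 × 0.4 + 4 × 0.8) / 18 = 0.489; variance = 1 + (14 × 0.16 + 4 × 0.64) / 18 − 0.489² = 1.028; d = 0.489 / 1.014 = 0.48.

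For case F the true and carried-forward means are equal. Only the SD differs, because the four imputed zeros have no spread. Cases E to H apply unchanged at posttreatment if the rule also fills missing posttreatment scores, so there too d can be overstated with no worsening (F, G). If the rule fills only 2-month scores, the posttreatment point falls away and the 2-month point stands.

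**Size against sampling error.** The approximate standard error of d at n = 18 is √(1/18 + d²/36). At d = 0.40 it is 0.245, so the shift of 0.08 in case A is about a third of a standard error. At d = 0.59 it is 0.255, so the shift of 0.21 in case D is about four fifths of one.

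**Responder rates and PGIC.** If responder rates are reported at 2 months, each late-lost responder who has relapsed adds 1/18 = 5.6 percentage points. The PGIC has no baseline score, so an early loss has nothing to carry.

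**The case against.** The assumption is stated openly beside the label. This is a small, uncontrolled pilot whose efficacy testing is declared limited, and Aim 1 is unaffected. Carrying baseline forward for early losses does pull the mean below the completers' mean if completers improved. The 2-month assessment is a remote questionnaire with a $25 payment, so late losses may be few. Case A needs four late losses, no early ones and half the gain gone, and even then shifts d by a third of a standard error. The planned RCT compares vEAET with an alternative, so a within-arm d is only an indirect input to its power analysis. All of this stands, and it limits the weight of the point. It does not justify the label.

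Three stronger or simpler readings are tempting, and the documents do not support them:

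- A reader might infer that the rule inflates the 2-month effect. Cases C and E go the other way, and the plan gives neither the timing of loss nor the durability of gains.
- A reader might take 25% as the expected share of missing follow-up data. It covers loss between consent and treatment start.
- A reader might infer that the rule overstates only if gains fade overall, or that it is safe at posttreatment unless dropouts worsen. The first holds only if lost and retained Veterans follow the same course (case D breaks it). The second can hold for the mean but fails for d (cases F and G).

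**Conclusion.** The concern holds in a limited form: the conservative label is not assured. At 2 months the rule can overstate, match or understate both the mean change and d, and on d it can also overstate at posttreatment. Neither the size nor the net direction can be fixed from the documents. The figures above rest on the assumed gain, SD, number lost and course of the lost Veterans, and show only that both directions are possible. The weight is minor to moderate. It is worth correcting because the 2-month effect is a stated aim, the effect sizes go forward to the RCT power analyses, and the plan reports nothing by which a reader could judge the label.

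**What to change.** Keep the paired tests and the d formula, and make these changes:

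1. Remove conservative as a description of the rule.
2. Report numbers observed and missing at each visit, split into lost before and lost after posttreatment.
3. Beside the carried-forward result, report 2-month mean change and d from observed cases and with baseline carried forward. In case A these give d of 0.40 and 0.35, against 0.48 carried forward and 0.40 true. State that baseline carried forward is not a bound on the mean (dropouts may worsen) or on d (imputed zeros shrink the SD): in case D it gives 0.66 against a true 0.59.
4. Name the visit for the 30%, 50% and 70% counts, and count missing as non-responder in any rate reported at follow-up.
5. For the PGIC, report the observed-case result and, as a separate row, the proportion improved among all starters with missing counted as not improved.

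The cost is a wording change and a few extra result rows; no new visit or measure is needed. The follow-up figures may look less favourable. Observed-case results assume that loss is unrelated to outcome and are less precise: with 14 of 18 Veterans the standard error grows by about √(18/14) = 1.13, or 13%.

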Study Design Overview. The proposed study is an uncontrolled pilot in which 18 Veterans age 60-95 years will undergo online Emotional Awareness and Expression Therapy delivered over video teleconference (vEAET). The aims are to evaluate the acceptability and feasibility of vEAET, to perform limited efficacy testing and evaluate effect sizes, and to select mediator/moderator measures for a subsequent RCT that will be part of a Merit Review application. Each Veteran will receive one 90-minute individual session of vEAET plus eight 90-minute weekly group sessions of vEAET, all delivered over VTC. The study will include 3 vEAET groups, each with 6 Veterans. We will use VVC as the primary VTC platform, with Zoom (San Jose, CA) as the back-up platform. For convenience in this pilot, the PI will administer vEAET sessions, with the possible addition of another therapist later, in which case the IRB will be contacted. Assessments will include satisfaction ratings, pain ratings, and psychosocial functioning, and will be performed at baseline, after the initial individual session, posttreatment, and 2-month follow-up. We will perform all assessments remotely using OutcomeMD (Los Angeles, CA), a secure, HIPAA-compliant, and VA-approved web-based platform. The goal is to perform the entire study remotely without any in-person visits.

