We plan to complete this pilot over a 12-month period. We anticipate consenting 24 and enrolling 18 Veterans. The IRB application will be submitted in June 2020. The first group is anticipated to begin in September 2020. The groups should be completed by the end of February 2021. We have allowed 3 months at the end of the study to carry out data cleaning and analysis and to begin abstract, manuscript, and grant writing. Please see

the timeline in **Table 2**. Unless participants give permission to bank their data for future research, it will be destroyed 6 years from the end of the fiscal year after completion of the research project.

Task Month	Jun	Jul	Aug	Sep	Oct	Nov	Dec	Jan	Feb	Mar	Apr	May
IRB application & approval	X	X										
Contact potential participants		X	X	X	X							
Enrollment/baseline assessments (n=12)			X	X	X	X						
vEAET				X	X	X	X	X	X			
Posttreatment assessments					X	X	X	X	X			
2-month follow-up assessments							X	X	X	X		
Interim and final data analyses							X	X	X	X		
Abstract and manuscript preparation										X	X	X
Prepare and submit Merit Review										X	X	X

7. References

3. Group TOTfCPW. VA/DoD Clinical Practice Guideline for Opioid Therapy for Chronic Pain. Washington, DC: VA/DoD; 2017 February 2017.
6. [name] BC, Lumley MA, Cassidy JT, Steers WN, Osato S, Schubiner H, et al. Emotional Awareness and Expression Therapy (EAET) Achieves Greater Pain Reduction than Cognitive Behavioral Therapy (CBT) in Older Adults with Chronic Musculoskeletal Pain: A Preliminary Randomized Comparison Trial. *Pain Med*. 2020;e-published ahead of Print.

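### Do the March end of 2-month follow-up in Table 2 and its n=12 label require a change to the plan?

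*Combined protocol and SAP*

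**What the plan says.** Section 6 sets out a 12-month project, June 2020 to May 2021. The first group is expected in September 2020, and "The groups should be completed by the end of February 2021". It adds "We have allowed 3 months at the end of the study to carry out data cleaning and analysis", with abstract, manuscript and grant writing to begin in the same period. On numbers it says "We anticipate consenting 24 and enrolling 18 Veterans".

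Table 2 marks these months:

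| Row | Months marked |
|---|---|
| Enrollment and baseline, labelled n=12 | Aug to Nov |
| vEAET | Sep to Feb |
| Posttreatment assessments | Oct to Feb |
| "2-month follow-up assessments" | Dec to Mar |
| "Interim and final data analyses" | Dec to Mar |
| Manuscript; Merit Review application | Mar to May |

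Elsewhere the sample is described the same way each time. Section 1 plans to consent up to 24 "with the goal of having 18 Veterans initiate vEAET treatment", and Section 3 (Study Design Overview) states "The study will include 3 vEAET groups, each with 6 Veterans".

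**The concern.** Two things in Section 6 do not agree.

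The first is the calendar. Treatment and posttreatment assessments run into February, so a 2-month follow-up counted from February belongs in April. Table 2 has no follow-up or analysis mark after March. If the final analysis were run in March as drawn, the last group's follow-up would be early or still pending. Aim 2 wants follow-up effect sizes for a later trial, and Section 5 says the data will inform its power analyses. The Analysis Plan carries the last observation forward only for values missing through attrition, so a visit not yet due has no stated handling.

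The second is the sample size. The row label "Enrollment/baseline assessments (n=12" (the table then closes the bracket) matches neither 18 nor 24. If 12 were the real target, the standard error of a mean change would be larger by √(18/12) = 1.22, or about 22%, for the same SD.

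**Working it through.** **Planned numbers.** Section 1 gives 18 starting treatment and at least 25% dropout. 18 / (1 − 0.25) = 24, which reproduces the consent target. Three groups × 6 = 18, which reproduces the treated number. The label 12 equals two groups of six. It is 6 below 18 and 12 below 24, and nothing in the text describes a subset of 12.

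**Lag within Table 2.** First marks: posttreatment October, follow-up December, a lag of 2 months. Last marks: posttreatment February, follow-up March, a lag of 1 month. The beginning of the follow-up row is right and the end is short.

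**Due dates, posttreatment date plus 2 calendar months:**

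| Last posttreatment date | Follow-up due | Days left to 31 May 2021 |
|---|---|---|
| 31 Jan 2021 | 31 Mar 2021 | 61 |
| 1 Feb 2021 | 1 Apr 2021 | 60 |
| 28 Feb 2021 | 28 Apr 2021 | 33 |

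The protocol states no visit window. Counted as 8 weeks (56 days), a 3 February finish is due on 31 March and a 28 February finish on 25 April. A late-February finish therefore lands in April on either count, while an early-February one may not.

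**Must the last group finish in February?** The sentence in Section 6 sets an outer limit. Table 2 closes enrollment in November. Assume the last group starts on 30 November 2020:

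- The eighth weekly session is 7 weeks later, on 18 January 2021, and follow-up is due on 18 March.
- If one further week is allowed for the individual session, treatment ends on 25 January and follow-up is due on 25 March.

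Both dates fit the March end of the table. The conflict therefore comes from the February marks themselves and not from the session count.

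**How many follow-ups could be affected?** One group is 6/18 = 33% of the treated sample, but that share holds only if exactly one group finishes in February. Section 6 gives no dates by group. A strictly back-to-back sequence from 1 September would start group three 16 weeks later, on 22 December. That sits poorly with enrollment closing in November and with posttreatment marks in every month from October to February. No share or number of days late can be derived from the documents.

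**What would the slip change?**

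- *Timing of follow-up.* The interval is set at 2 months in Sections 1 and 3 and in Table 1. Staff schedule the visit from each participant's own posttreatment date, not from a month-level chart.
- *Timing of the analysis.* There is no data cut-off. Section 6 reserves the last three months (March to May) for work that includes analysis, so waiting for an April visit stays within the plan.
- *Missing data.* A visit not yet due is not attrition, so the carry-forward rule does not reach it. An analyst would wait, or call an earlier look interim, which the table's row title already allows for.
- *Sample size.* The plan contains no power calculation, stopping rule or formula that takes 12 as an input.

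**The case for a change.** The strongest case for acting is that the table contradicts itself whatever the text says. February posttreatment marks need April follow-up marks, and there are none. The closing three months contain the April visits and do not come after them, so the time for final analysis shrinks to about a month. The analysis row is headed as covering the final analysis and stops in March. The n label is contradicted by the paragraph just above it, and correcting both would cost only a table edit.

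The factual part stands: the follow-up row is a month short at its end, and 12 is the wrong number for that row. The inference to harm does not stand. April visits leave May for the final analysis, inside the stated 12 months, and the analyses listed are descriptive statistics, paired t-tests, effect sizes and responder frequencies in about 18 people. Nothing ties the final analysis to March. Even the right replacement for 12 is uncertain: baseline assessment follows consent and precedes treatment, so the count for that row could lie anywhere from 18 to 24.

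**Conclusion.** Both observations are correct and both are clerical. Table 2 should have run follow-up past March if it meant its February posttreatment marks, and its n=12 agrees with nothing else in the protocol. No change to the plan follows. Section 6 is a forecast. The follow-up interval and the sample of 18 are fixed consistently elsewhere, and the closing months already have room for the final analysis: 33 days after the last follow-up in the latest case, a 28 February finish with calendar months. No endpoint, test, missing-data rule or effect size depends on either slip.

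This rests on two assumptions: that visits are scheduled from each participant's own posttreatment date, and that the final analysis waits for the last visit. Both are ordinary practice, and nothing in the documents points the other way. The share of follow-ups falling after March is not determinable, since no group dates are given.
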